Antibody response to HPV types 6, 11, 16 and 18 has been collected and analyzed on over 1500 serology samples for months 0, 7, 12, 18 and 24. Seroconversion rates at month 7 were approximately 93-98% in this HIV-positive population, much higher than anticipated. However, peak Geometric Mean Titres (GMT) were lower than in HIV negative populations. In addition this was associated with a significant decline in antibody levels by month 24, particularly to HPV18. Similar to our findings, Kahn et al., also showed that level of antibody was lower in individuals not on cART in their open label 16-23 year old study of 99 women given the q HPV vaccine.⁸⁰ Of note, we also observed statistically significantly higher levels of incident and persistent infections of vaccine containing types in a short term follow up period. This preliminary data outlines the importance of following this established cohort for long-term immunogenicity. When directly comparing the school based vaccine target age of 9-13 years, the HIV positive girls had a statistically significantly lower peak GMT than age matched HIV comparators.^{81,82} Similar studies conducted by other investigator groups have preliminary data available as well. Weinberg et al, showed that in HIV infected 7-12 year old children, there was a good seroconversion rate at > 94% but noted that the level of antibody to HPV18 was less than for the other genotypes. They also added a fourth dose of the vaccine which demonstrated an appropriate anamnestic response suggesting that should a booster be deemed necessary it should function to appropriately enhance the antibody response.⁸³ A South African based study of the bivalent vaccine demonstrated safety and 100% seroconversion to the vaccine containing serotypes regardless of CD4, HIV viral load and HIV clinical stage of disease.⁸⁴

Our study will ensure careful assessment and scrutiny of the health outcomes in HIV-positive girls and women who were able to access the HPV quadrivalent vaccine (GARDASIL™) in our previous study. We will be able to determine the value of this vaccine for sub-groups of girls and women with CD4 T cell depletion and variable HAART uptake. Most studies published to date on HPV vaccines have been, by necessity, supported by the vaccine manufacturing companies, and have excluded HIV-infected subjects. This study remains one of the few investigator-driven, peer-reviewed, independently funded vaccine studies, allowing for open scrutiny of vaccine efficacy and safety in a typically understudied population.

2.0 HYPOTHESIS

It is hypothesized that HPV antibody levels in HIV-positive girls and women will decline more rapidly and more significantly than in HIV-negative girls and women and this decline will be determined by HIV parameters.

3.0 OBJECTIVES

The overall goal of the study is to determine the immunogenicity and efficacy of the HPV vaccine out to 4 years in an established cohort of HIV-positive girls and women in Canada.

1. Primary

To measure the antibody response to each genotype contained in the qHPV vaccine out to 96 months post vaccination regimen.

2. Secondary

- 1) To determine the incidence rate and nature of 'breakthrough' HPV incident and persistent (2 sequential positive HPV DNA in > 6 months) infections of vaccine- non-vaccine-containing high-risk types;
- 2) To determine the incidence rate of cervical dysplasia (LSIL or greater) and/or vulvar and vaginal dysplasia associated HPV genotypes (both with and without vaccine- types); and
- 3) To determine the incidence rate of external genital warts.

3. Exploratory

- 1) To examine the relationship between HSV-2 serostatus and peak HPV antibody response as well as HPV incident and persistent infections;
- 2) To relate vaginal microbiome profiles to HPV acquisition/persistence and cervical dysplasia.

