| 18.4 | Publication Plan | 36 |
| 19.0 | REFERENCE LIST | 37 |

SUMMARY

| | |
|---------------------------|---|
| Title | Long Term Follow-up Study of CTN 236 - A Study of an HPV VLP Vaccine in a Cohort of HIV Positive Girls and Women |
| Goal | We hypothesize that HPV antibody levels in HIV-positive girls and women will decline more rapidly and more significantly than in HIV-negative girls and women and that this decline will be determined by HIV parameters. |
| Study population | HIV-positive girls and women (greater than, or equal to, age 11) attending the HIV treatment clinic that are currently enrolled in CTN 236 study will be invited to participate in the 5 year long term follow-up study. |
| Objectives | |
| Primary | To measure the antibody response to each genotype contained in the qHPV vaccine out to 96 months post-vaccination regimen. |
| Secondary | 
1) To determine the incidence rate and nature of 'breakthrough' HPV incident and persistent (2 sequential positive HPV DNA in > 6 months) infections of vaccine- non-vaccine-containing high-risk types;2) To determine the incidence rate of cervical dysplasia (LSIL or greater) and/or vulvar and vaginal dysplasia associated HPV genotypes (both with and without vaccine- types); and3) To determine the incidence rate of external genital warts. |
| Exploratory | 
1) To examine the relationship between HSV-2 serostatus and peak HPV antibody response as well as HPV incident and persistent infections; and2) To relate vaginal microbiome profiles to HPV acquisition/persistence and cervical dysplasia. |
| Timeline | First Visit, First Subject (FVFS): 10 June 2015 Last Visit, Last Subject (LVLS): 30 March 2019 |
| Study design | A longitudinal cohort follow up study of girls and women aged 11 years of age and older who participated in the study, "A Study of an HPV VLP Vaccine in a Cohort of HIV Positive Girls and Women (CTN 236)" |
| Inclusion Criteria | 
• Enrolled in CTN 236 study• Able to give fully informed consent or assent |

Research Protocol
Long Term Follow-up Study of CTN 236 - A Study of an HPV VLP Vaccine in a
Cohort of HIV Positive Girls and Women

| | |
|---|--|
| Exclusion Criteria | 
 • Did not receive at least one vaccination via CTN 236, phase 1 • Cannot provide fully informed consent or assent |

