Our study group was one of the first groups globally to study one of these vaccines in HIV-positive, immune compromised populations. As the qHPV vaccine GARDASIL™ (Merck), which contains subtypes 6 and 11 (responsible for 90% of genital warts) and subtypes 16 and 18 (responsible for 70% of cervical cancer) was the first to be licensed and available in Canada for post-licensure studies, we engaged with Merck to permit an initial study of the safety and immunogenicity of this vaccine in a cohort of HIV-positive girls and women. Data from this cohort has

provided valuable information about the health of Canadian women and girls living with HIV. At the initial screening visit more than 80% of subjects were negative to HPV genotypes 6, 11, 16 and 18, found in the qHPV vaccine. This was a higher seronegative rate than seen in a US based study in which only 55.6% were HPV 16 negative and 73.7% HPV 18 negative at baseline, despite being a younger cohort overall (N=99, mean age 21.4 years).⁷⁸ Preliminary data outlined that in our study, 17 % of HIV-positive women had low-grade squamous intraepithelial lesions (LSIL) or greater at screening and 29% had at least one strain of oncogenic HPV present. It was observed that greater numbers of oncogenic HPV types were present in those women with cervical dysplasia.⁷⁹

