12.1.3 HSV2 Serology Testing

Samples will be sent to the BCCDC Virology research laboratory, Vancouver, BC for analysis. The HerpeSelect ELISA (Focus Technologies) will be used but will employ a high cutoff index value of 3.5, which has been shown to offer improved specificity in the setting of HIV co-infection.^{87,88,89} Previously stored blood will be pulled as per protocol for baseline testing and at each study visit, participants will have serum stored for batched testing of HSV type-specific antibody. After baseline determination of serostatus for all participants, follow-up testing will be performed only on previously seronegative participants to assess for interval seroconversion.

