16.0 STATISTICAL ANALYSIS

1. Statistical Analysis Plan

Demographics: Characteristics of the study population will be described with frequencies and proportions for categorical variables, means and standard deviations for normally distributed continuous variables and medians and interquartile ranges for skewed continuous variables.

2. Primary Analysis

For each of the four vaccine containing HPV types, antibody response will be summarized using GMT's calculated for age specific groups within the HIV-positive cohort. Specific age groupings have been chosen to permit age matched HIV comparisons.

- a) Antibody response for subjects aged 9-13 and those aged 16-26 will be compared to the individual patient level data from an HIV-negative cohort 86 using Wilcoxon rank-sum tests. The age adjusted fold-difference in GMT

between HIV-positive and HIV-negative populations will be calculated using generalized linear models. For women over age 26, the type specific HPV GMT will be compared to GMTs in the published literature using a sign test.

- b) Within the HIV-positive cohort, predictors of decline from peak antibody response among HIV-positive girls and women will be determined using generalized linear models. Potential covariates to be considered in these models are age, HSV-2 status, substance use, CD4 count, HIV viral load and antiretroviral status at the time of first vaccination, and CD4 nadir.
- c) Longitudinal analyses will be conducted to describe the effect of HIV on antibody response at the visits at 36, 48, 60, 72, 84, and 96 months post first vaccine dose. Generalized estimating equation (GEE) models with a unity link will be used to adjust for correlation among repeat observations within study participants. Individual level data on HIV-negative girls and young women will be available at 36, 48, 60, 72, 84 and 96 months post first vaccine dose. After adjusting for age, an interaction between HIV and time since first dose will be included in the model to test for a difference in the degree of waning of response in addition to the strength of the initial response. GEE models will also be fit for the HIV-positive girls and women alone to examine the associations.

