- d) Predictors of HPV antibody seroresponse in our study population will be identified using logistic regression. This analysis is considered to be of vital importance as other vaccines have been shown to not be effective in subgroups of HIV positive individuals and could permit targeting of the proper population allowing for cost-effective use of this vaccine. The primary predictor of interest is CD4 count and justification for this is based on hepatitis B vaccination data described above. The secondary predictors of interest will include the variables: age, presence and number of strains of HPV, HIV viral load, use of HAART, use of injection drugs, and ethnicity. These predictors were chosen as ones that make the most clinical sense for potent impact on vaccine antibody response.

3. **Exploratory Analyses**

HSV analyses will employ linear or logistic regression models as appropriate, with HSV-2 serostatus as a time- updated primary predictor variable. To address these issues, we will quantify the impact of both incident (acquired within the past year) and prevalent (present at the time of diagnosis) HSV-2 co-infection on each of the primary HPV-related outcomes as described in preceding section (GMT, breakthrough HPV infections, genital tract dysplasia, and external genital warts).

Vaginal Microbiota Analysis. The output of the bioinformatics pipeline, including inventory of unique operational taxonomic unit (OTU) sequences, their taxonomic lineage and abundance, will be used to visualize and characterize the vaginal microbiota. Using various community-level analyses available as packages in R: 133

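### Does the persistent-infection rule need a written baseline before breakthrough HPV infections can be counted?

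*Combined protocol and SAP*

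**What the plan says.** Section 3.0 gives the working rule within secondary objective 1: "HPV incident and persistent (2 sequential positive HPV DNA in > 6 months) infections of vaccine- non-vaccine-containing high-risk types". The Summary repeats it: "persistent (2 sequential positive HPV DNA in > 6 months) infections". Section 1.0, item 2, has a similar background definition, two consecutive PCR positives 6 months apart. None of these mentions an earlier negative. Breakthrough is used in the Summary, section 3.0 and section 16.3, and defined in none of them.

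Section 16.2 covers antibody outcomes only ("For each of the four vaccine containing HPV types, antibody response will be summarized using GMT's"). Section 16.3 nonetheless refers back to "primary HPV-related outcomes as described in preceding section (GMT, breakthrough HPV infections, genital tract dysplasia, and external genital warts". GMT is in 16.2; the other three outcomes are not.

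For HSV-2 the protocol is explicit. Section 12.1.3 says "Previously stored blood will be pulled as per protocol for baseline testing" and then "follow-up testing will be performed only on previously seronegative participants to assess for interval seroconversion". No matching sentence exists for HPV DNA, although section 1.0, item 10, shows that CTN 236 produced such results: at screening "29% had at least one strain of oncogenic HPV present", and in follow-up the group saw "statistically significantly higher levels of incident and persistent infections of vaccine containing types".

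Participants have up to three annual visits (Summary; section 11.0), each within 2 months either side of its target (section 7.4.2).

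**The concern.** On follow-up samples alone, a newly acquired persistent infection needs the pattern negative, positive, positive. A woman with two samples can never show it. A type positive at the first two follow-up visits meets the persistence rule, but its onset is unknown: it may have been acquired after vaccination or have been present before it.

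One analyst might count every same-type pair and another only pairs preceded by a negative. If the counts differed twofold or more, a named secondary outcome would depend on an unwritten choice, and infections present before vaccination could be reported as vaccine failures. The outcome is also reused in the HSV-2 and microbiome analyses. The care taken over the HSV-2 baseline makes the silence on HPV DNA look like an oversight.

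**Working it through.** The plan gives no event count, rate or power for this outcome, so there is no figure to reproduce. The check sizes the ambiguity and then asks which reading the text supports.

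**Inputs.** Three annual samples (Summary; section 11.0). Adjacent visits are 12 ± 4 = 8 to 16 months apart, so every adjacent pair satisfies the 6-month condition. Prevalence of any oncogenic type is 29% (section 1.0, item 10). Treating the 12 high-risk and probably high-risk types of section 1.0, item 1, as equal and independent (assumption), prevalence per type is p = 1 − 0.71^(1/12) = 0.0281. Mean duration d: section 1.0, item 2, gives 5–6 months for low-risk and 8–14 for high-risk types in HIV-negative women, so 5.5, 11 and 14 are used. The value 24 is an assumption for the slower clearance in HIV noted in item 5.

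**Step 1: raw counts.** In a steady two-state model, the probability that a positive type is positive again a year later is r = p + (1 − p)·exp(−12/[d(1 − p)]).
- Share of qualifying infections positive at entry: 1/(2 − r), never below one half.
- All qualifying infections against negative-positive-positive: (2 − r)/(1 − r), never below 2.

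**Step 2: matched person-time.** All pairs can arise from two intervals, negative-positive-positive from only one. The ratio of rates is therefore half the ratio of counts.

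| d (months) | r | Share positive at entry | Ratio of counts | Ratio of rates |
|---|---|---|---|---|
| 5.5 | 0.131 | 53% | 2.15 | 1.08 |
| 11 | 0.344 | 60% | 2.53 | 1.26 |
| 14 | 0.430 | 64% | 2.76 | 1.38 |
| 24 | 0.609 | 72% | 3.56 | 1.78 |

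The lower bound of one half needs constant persistence as well as constant prevalence. With prevalence fixed at 10% and annual persistence rising from 0.3 to 0.6, the share is 0.03/(0.03 + 0.06 − 0.018) = 42%. If acquisition doubles at entry, it is 37% (d = 5.5), 44% (11) or 56% (24).

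**Step 3: using CTN 236 screening results.** Take the first follow-up sample as 36 months after screening. The probability of having been positive at screening is q = p + (1 − p)·exp(−36/[d(1 − p)]) for a type positive at entry, and p(1 − q)/(1 − p) for a type negative at entry.
- d = 11: q = 0.0616 and 0.0272. Weighted: 0.604 × 0.0616 + 0.396 × 0.0272 = 0.048, so 95% were type-negative at screening.
- d = 24: q = 0.236 and 0.022. Weighted: 0.719 × 0.236 + 0.281 × 0.022 = 0.176, so 82% were type-negative.

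Most infections already positive at entry are therefore datable to after screening once the CTN 236 result is consulted.

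**Step 4: which reading the text supports.** The title calls this a long-term follow-up of CTN 236. Visits begin at number 8 and are timed from first dose (section 7.3). Participant numbers carry over (section 7.0, item 1). Section 16.2(b) already needs CTN 236 data, namely peak response and CD4 count at first vaccination. Incidence rate, incident and breakthrough all mean new infection, and a type positive before vaccination is none of these. The same group has already reported incident and persistent infections in CTN 236, so it has classified such infections before.

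**Cross-reference in 16.3.** Its four outcomes match the primary objective and the three secondary objectives of section 3.0, in the same order. A reader can tell what is meant.

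**The case for a change.** The strongest reply is that incidence does not say new since when: since vaccination, since a CTN 236 sample, or since the first follow-up visit. That is true, and the text does not settle it.

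The choice weighs most on vaccine types. If vaccination cuts acquisition by 50–90% (an assumption, not in the documents), 7–21% of qualifying infections at d = 11, or 29–66% at d = 24, are in women type-positive at screening. These shares are large because the total becomes small. For types 16 and 18 together, at the assumed per-type prevalence, they amount to about 0.1 per 100 women at d = 11 (407 × 0.1/100 = 0.4 in the whole cohort) and 0.8 per 100 at d = 24 (407 × 0.8/100 = 3.3), if every woman gave three samples. Consulting the screening result identifies them.

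The matched-rate ratio can also exceed 1.8 if infections last longer: at r = 0.8 it is (2 − 0.8)/(2 × 0.2) = 3.0. That contrast still requires both analysts to ignore CTN 236.

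Handling of a missed or β-globin-negative sample between two positives is unwritten as well. Section 13.0 calls such a sample inadequate, so it should not be read as a negative. A missed middle visit leaves 24 ± 4 = 20 to 28 months between positives. Re-infection would then explain 9–21% of such pairs at d = 11 and 1–3% at d = 24, but 49–82% at d = 5.5. The last figure reflects the duration given for low-risk types, whereas the objective centres on vaccine and high-risk types.

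What stands is that the documents do not show when CTN 236 genital samples were taken or how many women lack one. Some pairs will have unknown onset under any rule.

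**Conclusion.** The omission is real, but it is missing detail and does not call for a change. The twofold contrast compares raw counts under two readings that both discard the parent study's HPV DNA results. Matching person-time brings it to about 1.1–1.8 for mean durations of 5.5 to 24 months. Using the CTN 236 screening result leaves 5% (11 months) to 18% (24 months) of qualifying infections in women already type-positive at screening. Those figures assume steady prevalence and persistence, 12 equal and independent types, a 36-month gap from screening to first follow-up sample and no vaccine effect; the 24-month duration is not in the documents.

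The wording of the objective, the continuity with CTN 236 and the group's earlier reporting of the same outcomes all point analysts to the sensible reading. The loose reference in section 16.3 is a clerical slip. The outcome is a descriptive secondary one with no stated test or power, and the primary antibody analysis does not depend on it.

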8.0 MANAGEMENT OF CERVICAL CYTOLOGIC ABNORMALITIES

All participants (except those pre-menarchal and not yet sexually active) will undergo clinical standardized Pap smear testing as per local site standards. Cytologic abnormalities will be managed according to local algorithms. Management of cervical cytologic abnormalities will be decided by the Site Investigator and may be based on the clinical standardized Pap smear or study cervical cytologies when available. It is suggested to manage abnormal results based on the higher grade of dysplasia.

Participants who have high grade or persistent low grade changes will be referred for follow-up evaluation by colposcopists involved with local HIV treatment centres. After obtaining consent to release medical records, all colposcopic, colpophotographic and histopathologic (biopsy) results will be added to the study record; slides from biopsies will be requested by the BC Cancer Agency for central confirmation of histopathologic diagnoses. Invasive cancers diagnosed during the study will be carefully documented and recorded once local, appropriate clinical management is provided. As in previous multicentre studies of high risk HIV positive women, we acknowledge variation in local colposcopic and treatment algorithms and anticipate imperfect compliance with referral for colposcopy; similarly, cervical disease endpoints (squamous intraepithelial neoplasia or dysplasia) in this study are cytologically and/or histologically defined as appropriate. Histopathology will be reported as cervical intraepithelial neoplasia grades, 1, 2 or 3 (CIN 1, 2 or 3), or carcinoma in situ.

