The PreservCyt vial will be processed for cytologic evaluation following the ThinPrep protocol (Cytac Incorporated). Slides will be read by cytotechnologists at the Cervical Cancer Screening Laboratory (CCSL) of BC. Reporting rules for normal and abnormal results will be the same as for routine specimens processed at the CCSL, a facility that processes all cervical smears performed in British Columbia (up to 600,000 per year). Standard reporting of Pap smears will be according to the Bethesda criteria e.g. low grade and high grade squamous intraepithelial neoplasia (SILs)

3. **Vaginal Microbiota Analyses – [name] Lab, University of Saskatchewan**

Vaginal samples will be collected for microbiome analysis as per the VOGUE Emerging Team Grant protocol (CIHR FRN 108030; PI [name]). Samples will be transported to the [name] laboratory at the University of Saskatchewan, where total DNA will be extracted from vaginal swabs using the MagMAX magnetic DNA binding platform (Applied Biosystems). Chaperonin 60 (cpn60) amplicons¹³⁰ will be then prepared as previously described utilizing multiplexed ID sequences (MID) to pool samples during sequencing.⁹⁰ Sequencing will be performed on the Roche GS Junior pyrosequencer in the [name] lab. Raw sequence data will be processed initially using the standard on-rig software tools for quality control and filtering. Quality filter-passed read data will then be analyzed using the mPUMA bioinformatics pipeline developed by the [name] lab.⁹¹

14.0 **TRANSPORTATION OF LABORATORY SAMPLES**

All shipments of serum samples and vaginal microbiota swabs are to be shipped frozen and prepared by qualified individuals ensuring that all shipments are packed and shipped according to IATA regulations and are to be packed using dry ice.

All shipments of liquid based cytology are to be shipped ambient and prepared by qualified individuals ensuring that all shipments are packed and shipped according to IATA regulations.

All samples are to be clearly labeled with subjects' 5 digit PID#, date of collection, and visit month.

All shipments must have an accompanying biological shipment listing, with a copy being retained at the site. A biological shipment listing template will be provided to the sites by the Study Coordinating Centre.

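### Secondary objective 2 covers vulvar and vaginal dysplasia, but these sites have no case definition, reporting category or biopsy-retrieval route of their own, and HPV is typed only on the cervical sample

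*Combined protocol and SAP*

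**What the plan says.** The Summary and Section 3.0 both give secondary objective 2: "To determine the incidence rate of cervical dysplasia (LSIL or greater) and/or vulvar and vaginal dysplasia associated HPV genotypes", with and without vaccine types. Section 16.0, item 3 (Exploratory Analyses), relates HSV-2 status to outcomes that include "genital tract dysplasia, and external genital warts".

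Section 8.0 is headed as the management of cervical cytologic abnormalities. Its entry point is: "Participants who have high grade or persistent low grade changes will be referred for follow-up evaluation by colposcopists involved with local HIV treatment centres". Once consent to release records is given, "all colposcopic, colpophotographic and histopathologic (biopsy) results will be added to the study record", and biopsy slides are requested for central confirmation. The endpoints that the section names are cervical, and "Histopathology will be reported as cervical intraepithelial neoplasia grades, 1, 2 or 3 (CIN 1, 2 or 3), or carcinoma in situ".

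Sections 7.4.3 and 7.5.6 provide, at each visit with a pelvic examination, an external genital examination and a visual inspection of the vagina and cervix. The one standardised tool mentioned is for genital warts. Each visit also updates the health history.

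Sections 7.5.7.1 and 13.0 (item 1) take the HPV DNA specimen from the cervix. In Section 13.0 (item 3), "total DNA will be extracted from vaginal swabs" for microbiota sequencing. No HPV typing of those swabs or of biopsy tissue is described.

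**The concern.** The objective names three sites, and the procedures are built for one. Cervical disease has scheduled cytology, a referral step, histology grades and central slide review. Warts have a standardised assessment. Vulvar and vaginal dysplasia has only general inspection and history-taking, with nothing to say what counts as a case or how it is graded or confirmed.

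At stake is how a low count would be read. Background item 3 reports a 4.2-fold higher rate of HPV-associated female genital cancer in HIV-positive women than in the general population. In such a cohort, few vulvar or vaginal cases after vaccination could be taken as good news when part of the explanation is incomplete ascertainment. Background item 1 shows that the investigators recognise this kind of limit: they decline to study anal and oral HPV because those sites were not evaluated at baseline.

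**Working it through.** The plan states no expected rate, event count or power for this endpoint, so there is no figure to reproduce. The check is a trace of the objective through each step.

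| Step | Cervix | Vulva and vagina |
|---|---|---|
| Examination (7.4.3, 7.5.6) | Inspection, study cytology, clinical Pap | Inspection; standardised tool for warts only |
| Referral that opens record retrieval (8.0) | High-grade or persistent low-grade changes | None written |
| Biopsy results and slides (8.0) | Retrieved, centrally confirmed | Retrieved if taken at a referred colposcopy; otherwise no route written |
| Endpoint definition (8.0) | Cytological and/or histological | None |
| Histology categories (8.0) | CIN 1, 2, 3 | None; carcinoma in situ is listed without a site |
| HPV typing (7.5.7.1, 13.0) | Endocervical PreservCyt aliquot | None; vaginal swabs go to microbiota work |
| Analysis (16.0) | No incidence analysis for objective 2; part of the undefined term genital tract dysplasia | Same |

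**Three cases followed through the text**

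1. Qualifying cervical cytology, with a vulvar or vaginal biopsy at the resulting colposcopy: the result enters the record and the slide can be reviewed. No vulvar or vaginal grade exists to report it under.
2. Normal cervical cytology, with a vulvar or vaginal lesion biopsied in routine care: the history update may reveal it. No step retrieves the report or slide, and no category receives it.
3. A lesion seen at a study visit and not biopsied: it may be noted, but no definition says whether it is a case.

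**What this does to the rate.** Let r be the share of true cases biopsied at a colposcopy reached through cervical referral, and c the share of the remaining cases that surface through inspection or history. Leaving false positives aside:

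recorded rate = true rate × [r + (1 − r) × c]

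Only the r part has a written route to central confirmation. The documents give neither r nor c. Taking each anywhere from 0 to 1 (assumption), the multiplier runs from 0 (r = 0, c = 0) to 1 (r = 1 or c = 1). The likely direction is downward; the size is undetermined. The number of cases cannot be projected either: 407 women are to be offered participation (Section 5.0), but no lesion rate is stated.

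**Genotypes.** The only typed specimen is endocervical. A type linked to a vulvar or vaginal lesion is therefore the type found on the cervix at about that time. Whether the lesion carries it is not observed.

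**The case against.** The strongest reply is that the plan does look at these sites. The external genital examination includes wart assessment without being confined to it, the vagina is inspected, further assessments are allowed where clinically indicated, and a lesion biopsied outside the study is a new health issue for the history update. Section 8.0 sets no anatomical limit on the biopsy results that it collects. All of this stands. A reader might infer that the incidence for these sites cannot be obtained at all, or that record collection is restricted to the cervix; the documents support neither.

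A reader might also try to put a factor on the understatement by assuming what share of affected women have abnormal cytology. That only restates the assumption, and it ignores cases found by inspection or history.

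On genotypes, the objective does not expressly promise typing of lesion tissue, so concurrent cervical types may be what was meant. That is a fair reading, but the plan does not say so, and the wording ties the genotypes to dysplasia at these sites.

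The and/or in the objective permits a composite. With 17% of women at LSIL or greater at screening (Background item 10), cervical events would probably dominate it and missed cases at other sites would shift it little. That limits the harm to a composite, but such a composite would then say almost nothing about the vulva and vagina.

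Finally, the CRFs, questionnaire, wart tool and laboratory manual are not among the documents, and a lesion field may already exist. That bears on the field alone. The case definition, categories and typing specimen belong in the protocol.

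**Conclusion.** The point holds in limited form. As written, vulvar and vaginal dysplasia is claimed in objective 2 and falls within genital tract dysplasia, yet it has no case definition, no vulvar or vaginal reporting category, and no route to retrieve and confirm a biopsy that does not start from abnormal cervical cytology. Incidence at these sites can be obtained only unsystematically and is probably understated, by an amount that the documents do not allow one to quantify. Lesion-specific genotypes for the vulva and vagina cannot be obtained from the procedures described.

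This rests on the protocol text alone and assumes that no unseen form or manual supplies a definition or lesion typing. It affects one part of one secondary objective and one exploratory outcome; the primary antibody objective is untouched. It should be corrected because the remedy is cheap and decides whether any statement about these sites can be made.

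**What to change.** Either of two changes removes the mismatch.

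**Keep the sites.**
- Extend the record release and central slide confirmation in Section 8.0 to any vulvar or vaginal biopsy already done in routine care, whatever the cervical cytology.
- Add vulvar and vaginal intraepithelial neoplasia as reporting categories, and use them to define the case and the term genital tract dysplasia.
- Record vulvar/vaginal lesion yes/no at the pelvic examination, if the CRF does not already do so.
- State that genotypes reported with these lesions are concurrent cervical genotypes.

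**Or narrow the claim.** Limit objective 2 (Summary and Section 3.0) and genital tract dysplasia (Section 16.0) to cervical dysplasia.

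The first option costs a few extra pathology reports and slides, possibly one CRF field, and a protocol amendment through the site ethics boards (Section 18.0), with a check that the records consent covers these reports. It adds no procedure and leaves referral, biopsy and treatment decisions as they are. The second costs only the amendment.
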